**Appendix 7- Positive Screen Criteria for Part 2**

38

AE	Adverse Event
ART	Anti-retroviral Therapy
BMI	Body Mass Index
CBC	Complete Blood Count
CD4	helper T lymphocytes positive for surface glycoprotein CD4
CI	confidence interval
CMP	Complete Metabolic Panel
COB	Cobicistat
DRV	Darunavir
FDC	fixed dose combination
FTC	Emtricitabine
HBsAg	hepatitis B virus surface antigen serology
HBV	hepatitis B virus
HCV	hepatitis C virus
HCV Ab	Hepatitis C virus antibody
HIV	Human Immunodeficiency Virus-1
HIV-SI	HIV Symptom Index
IRB	institutional review board
MAAS	Midland Antiviral Adherence Survey
PII	Personal Identifying Information
PRO	Patient Reported Outcome survey
STR	Single Tablet Regimen
TAF	tenofovir alafenamide
SEA	Serious Adverse Event
VL	viral load

## 1. Introduction

Human Immunodeficiency Virus-1 (HIV) is a life threatening and serious infection throughout the world. The World Health Organization estimates between 30-43 million people are living with HIV worldwide. The natural progression of the disease cripples the immune system, leading to unchecked infections and ultimately death.

With the advent of anti-retroviral therapy, HIV transformed from a terminal infection into a manageable chronic disease for patients who were able to obtain medications, provided they could remain adherent to them.

When single tablet regimens (STR) became available, adherence to HIV medications was made easier for many patients. However even years after STR became available, 38% of patients reported they do not maintain optimal adherence to their HIV medications. While there are many factors that contribute to this problem, medication intolerance contributes to suboptimal adherence for many patients.

## 2. Rationale for the Study

Darunavir/cobicistat/emtricitabine/tenofovir alafenamide (DRV/COB/FTC/TAF) is a coformulated STR, is the only protease inhibitor based STR, and is noted for its high tolerability. These traits have the potential to improve adherence in patients who have intolerance to the integrase inhibitor class. We propose a two part study design to evaluate if patients who have suboptimal adherence due to integrase inhibitor intolerance may better tolerate Syntuza and subsequently have improved adherence.

## 3. Study Objectives

### 3.1. Part 1

#### 3.1.1. Primary Objectives

3.1.1.1. To assess degree of adherence to ART in a real world setting

#### 3.1.2. Secondary Objectives

3.1.2.1. To evaluate trends and patterns in subjects who report suboptimal adherence

### 3.2. Part 2

#### 3.2.1. Primary Objectives

3.2.1.1. To determine potential changes in ART adherence in subjects who report suboptimal adherence due to side effects from integrase containing regimens switching to Symtuza.

#### 3.2.2. Secondary Objectives

3.2.2.1. To evaluate the tolerability of switching from integrase containing regimen to Symtuza with the aid of Patient Reported Outcomes (PRO) questionnaire and number of drug discontinuation for any reason

3.2.2.2. To determine the safety of switching from integrase containing regimen to Symtuza in subjects with HIV-1 infection as determined by the proportion of participants with virologic failure, a change in laboratory parameters, and change in CD4 cell count from baseline.

3.2.2.3. To evaluate for potential weight loss when switching from integrase containing regimen to Symtuza

## 4. Study Endpoints

### 4.1. Part 1

#### 4.1.1. Primary Endpoint

4.1.1.1. Percentage of subjects reporting suboptimal adherence

#### 4.1.2. Secondary Endpoint

4.1.2.1. Percentage of subjects who report suboptimal adherence due to tolerance issues/side effects

4.1.2.2. Percentage of subjects who report suboptimal adherence due to reasons other than tolerance issues/side effects

### 4.2. Part 2

#### 4.2.1. Primary Endpoint:

4.2.1.1. Change in adherence from baseline to 4 months, measured by adherence surveys

#### 4.2.2. Secondary Endpoints:

4.2.2.1. Change at 4 months from baseline in tolerability measured by standardized patient reported outcome questionnaire

4.2.2.2. Proportion of subjects that have HIV-1 RNA  $\geq$  50 copies/mL at baseline and at Week 16

4.2.2.3. Proportion of subjects with significant changes at 4 months from baseline in serum creatinine, AST or ALT

4.2.2.4. Change at 4 months from baseline in absolute and percentage CD4.

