## 5. Study Drug

### 5.1. Formulation

**5.1.1.** SYMTUZA (darunavir, cobicistat, emtricitabine, and tenofovir alafenamide) is an FDA approved fixed-dose combination tablet complete regimen for the treatment of HIV-1 infection in adults: • who have no prior antiretroviral treatment history or • who are virologically suppressed (HIV-1 RNA less than 50 copies per mL) on a stable antiretroviral regimen for at least 6 months and have no known substitutions associated with resistance to darunavir or tenofovir.. • Darunavir is an inhibitor of the HIV-1 protease. • Cobicistat is a mechanism-based inhibitor of cytochrome P450 (CYP) enzymes of the CYP3A family. • Emtricitabine, a synthetic nucleoside analog of cytidine, is an HIV nucleoside analog reverse transcriptase inhibitor (HIV NRTI). • Tenofovir alafenamide, an HIV NRTI, is converted in vivo to tenofovir, an acyclic nucleoside phosphonate (nucleotide) analog of adenosine 5'-monophosphate. SYMTUZA tablets are for oral administration. Each tablet contains darunavir ethanolate equivalent to 800 mg of darunavir, 150 mg of cobicistat, 200 mg of emtricitabine, and 11.2 mg of tenofovir alafenamide fumarate equivalent to 10 mg of tenofovir alafenamide. The tablets include the following inactive ingredients: colloidal silicon dioxide, croscarmellose sodium, magnesium stearate, and microcrystalline cellulose. The tablets are film-coated with a coating material containing polyethylene glycol (macrogol), polyvinyl alcohol (partially hydrolyzed), talc, titanium dioxide, and yellow ferric oxide.

**5.1.2.** Syntuza will be considered investigational in this study for those patients who are not virally suppressed at study entry.

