#### **7.7. Criteria for discontinuation of study drug**

- 7.7.1. In the event of the following, study drug will be discontinued: unacceptable toxicity, subject request for any reason, pregnancy, development of active tuberculosis, discontinue of the study at the request of the IRB
- 7.7.2. In the event of the following, study drug may be discontinued: in the event of significant new illness that compromises the ability to assess end points, lack of efficacy, subject noncompliance.
- 7.7.3. In the event that study drug is discontinued, every attempt should be made to keep the subject in the study and continue to perform the required follow ups and procedures through to the Week 16 Visit

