#### **7.8. Management of viral rebound**

7.8.1. At any post baseline visit either (1) an HIV-1 RNA  $\geq$  50 copies/mL for subjects who were  $<50$  at baseline or (2) an increase by 1 log for subjects who were  $\geq 50$  copies at baseline, will be repeated for confirmation within 4 weeks of the original test result. If confirmatory testing is  $\geq 200$ , HIV-1 genotype will be performed on the confirmatory sample. Subject may be withdrawn from the study at investigators discretion if resistance suggested by results. If no resistance is found, repeat viral load should be repeated again 4 weeks later.

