#### 8.2.2.1. Primary Endpoint

8.2.2.1.1. Percentage of subjects reporting suboptimal adherence, analyzed by intention to treat, from baseline to 16 weeks.

8.2.2.1.1.1. *We hypothesize that a minimum of 85% of subjects taking DRV/COB/FTC/TAF will demonstrate an optimal adherence score from baseline to four-months as measured by the Midland ART Adherence Survey.* Optimal adherence is defined as a Rasch score greater than or equal to 90%. Rasch scores range from 0% (no adherence) to 100% - (perfect adherence).

8.2.2.2. Secondary Endpoints. These are descriptive endpoints so no hypotheses are tested.

8.2.2.2.1. Change at 4 months from baseline in tolerability measured by standardized patient reported outcome questionnaire

8.2.2.2.2. Percentage of subjects with greater than or equal to 90% by pill count

8.2.2.2.3. Proportion of subjects that have HIV-1 RNA  $\geq 50$  copies/mL at baseline and at month 4

8.2.2.2.4. Proportion of subjects with significant changes at 4 months from baseline in serum creatinine, AST or ALT

8.2.2.2.5. Change at 4 months from baseline in absolute and percentage CD4.

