## 8.7. Part 2 - Analysis of Secondary End-Points

### 8.7.1. These are descriptive endpoints so no hypotheses are tested.

- 8.7.1.1. Change at 4 months from baseline in tolerability measured by standardized patient reported outcome questionnaire.
- 8.7.1.2. Percentage of subjects with greater than or equal to 90% by pill count
- 8.7.1.3. Proportion of subjects that have HIV-1 RNA  $\geq$  50 copies/mL at baseline and at month 4
- 8.7.1.4. Proportion of subjects with significant changes at 4 months from baseline in serum creatinine, AST or ALT
- 8.7.1.5. Change at 4 months from baseline in absolute and percentage CD4.
- 8.7.1.6. Change at 4 months from baseline in absolute and percentage weight
- 8.7.1.7. Number of drug discontinuation for any reason

8.7.2. All data will be summarized. For baseline characteristics and safety outputs a total overall column will be included to summarize all subjects. Data will be summarized by visit. In summary tables of continuous variables, the arithmetic mean (AM), median, 95% confidence interval (CI), standard deviation (SD) and standard error (SE) will be presented to one more decimal place than the original data. In summary tables of categorical variables, counts and percentages will be used.

8.7.3. We will identify and classify the case mix or heterogeneity of subjects adherence we will use latent class analysis (LCA); which allows us to identify a finite number of latent subgroups and to explore how treatment effect varies across these subgroups. Using the clinical, psychosocial and demographic variables we will classify subjects into latent homogenous classes based on similar response patterns.

8.7.4. Using the latent classes identified above we will use class membership (latent class) in a as a predictor of a distal standardized outcome adherence range from 0 to 100.

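### The virologic safety objective asks for the proportion with virologic failure, which is undefined, while its only endpoint pools suppressed and viraemic entrants and so mixes new failures with persistent viraemia

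*Protocol*

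**What the plan says.** **Objective.** Section 3.2.2.2 assesses the safety of moving from an integrase regimen to the study drug "as determined by the proportion of participants with virologic failure", together with laboratory and CD4 changes. No section of the protocol says what virologic failure is.

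**Endpoint.** Section 4.2.2.2 takes the proportion of subjects at or above 50 "copies/mL at baseline and at Week 16". Sections 8.2.2.2.3 and 8.7.1.3 repeat it as "copies/mL at baseline and at month 4". None of the three splits it by baseline status or frames it within subject. The neighbouring laboratory, CD4 and weight endpoints (4.2.2.3 to 4.2.2.5) are framed as changes from baseline. Section 8.7.1 adds: "These are descriptive endpoints so no hypotheses are tested".

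**Population.** The criteria in 6.2.3 set no viral-load limit. Section 5.1.2 says that the drug "will be considered investigational in this study for those patients who are not virally suppressed at study entry". Section 6.2.4.1.1 calls for a genotype before enrolment when the last result was not suppressed; it does not exclude such subjects.

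**Rebound rule.** Section 7.8.1 has separate triggers for a repeat test: reaching 50 for those below 50 at baseline, and a 1-log rise for those at or above 50. It guides patient management and is linked to no endpoint.

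**The concern.** Failure after a switch happens within a subject and means different things by starting point. A subject who enters suppressed can lose control. A subject who enters viraemic can fail to gain it. One pooled share at each of two visits does not separate these.

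Viraemic entrants are likely, because Part 2 enrols people who report missing doses. The pooled share could fall because viraemic entrants suppress, even while suppressed entrants rebound on the new regimen. A reader of the report could then take a falling share as evidence that the switch was virologically safe for patients who had control before it.

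**Working it through.** **The plan's own figure.** No rate, margin or precision is stated for this endpoint. The only computed design figure is the sample size in 8.8.2: ln(1 − 0.95)/ln(1 − 0.10) = 28.43, which rounds up to 29 against the stated 30. That is close enough, and nothing below depends on the difference. The target of 30 (6.2.2.1) is used as the denominator.

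**What two pooled shares can identify.** Let *b* be the number at or above 50 at baseline, *w* the number at or above 50 at Week 16, *x* the new failures among the 30 − *b* suppressed entrants, and *s* the viraemic entrants who suppress. Assume all 30 have both values. Then:

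- *w* = (*b* − *s*) + *x*
- change in share = (*x* − *s*)/30
- for given *b* and *w*, *x* can lie anywhere from max(0, *w* − *b*) to min(*w*, 30 − *b*)

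**Two courses with the same reported result** (assumed: 12 viraemic, 18 suppressed):

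| | Suppress, of 12 | Rebound, of 18 | Baseline share | Week 16 share | Failure among suppressed entrants |
|---|---|---|---|---|---|
| A | 10 | 4 | 12/30 = 40% | (2 + 4)/30 = 20% | 4/18 = 22% |
| B | 6 | 0 | 12/30 = 40% | (6 + 0)/30 = 20% | 0/18 = 0% |

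**Other splits.** The protocol gives no baseline split, so these are also assumptions:

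- 6 viraemic, 5 suppress, 5 of 24 fail (20.8%): the share is 6/30 = 20.0% at both visits, with no apparent change.
- 10 viraemic, 8 suppress, 4 of 20 fail (20%): 33.3% falls to 20.0%.
- 15 viraemic, 12 suppress, 3 of 15 fail (20%): 50.0% falls to 20.0%.
- With *b* = 10 and *w* = 6, new failures may be anything from 0/20 (exact 95% interval 0 to 16.8%) to 6/20 (30%; 11.9 to 54.3%).
- With few viraemic entrants the range closes. For *b* = 2 and *w* = 3, *x* is 1 to 3 of 28, that is 3.6% to 10.7%.

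**The other reading of the wording.** If the endpoint meant at or above 50 at both visits, it would count *b* − *s*: 1, 2 and 3 subjects in the first three examples above. That is persistent viraemia only and contains no new failure. This reading does not help either.

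**The case against.** **What stands.** The endpoint is secondary and descriptive, and 8.7.2 summarises data by visit, so two shares side by side is the natural reading. On that reading a rebounder still viraemic at Week 16 is counted: all four in course A are inside the 20%. They are mixed with others, not absent. Viral load is recorded per subject, and a separate SAP could add a transition table. This limits the weight of the point. It does not remove it, because the protocol fixes the unstratified share in three lists and leaves the term in its objective undefined.

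**Stronger readings that a reader might infer, and that the documents do not support:**

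- *That the endpoint cannot answer the objective at all.* The objective speaks of participants, and the Week 16 share does bear on it. What is missing is the separation of new failure from persistent viraemia.
- *That 7.8.1 already defines failure by baseline group.* It sets triggers for a repeat test and a genotype. It does not use the term.
- *That 7.8.1 and 7.7.3 contradict each other.* Section 7.8.1 says: "Subject may be withdrawn from the study at investigators discretion if resistance suggested by results". Section 7.7.3 says that "every attempt should be made to keep the subject in the study", but it applies when study drug is stopped. For that situation, 6.2.4.8 states retention and possible withdrawal together, so the two can coexist.
- *That withdrawals would lower the reported share*, for example from 6/30 to 4/28 = 14% if two rebounders left course A. That assumes they leave the denominator. The protocol states no such rule, and the intent-to-treat dataset (8.3.3.1) covers everyone enrolled.

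**Conclusion.** The point holds in a limited form. The objective rests on an undefined term, and the endpoint that serves it is pooled over two groups for which failure differs. The Week 16 share mixes new failures with persistent viraemia, and the change from baseline nets new failures against new suppressions. This follows from the structure of the endpoint and needs no assumption beyond a mixed population, which the protocol itself foresees.

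The size does rest on assumptions. With 12 of 30 viraemic, the same 40% to 20% fits 22% or 0% failure among suppressed entrants. If nearly all enter suppressed, the ambiguity is small. The correction should be made because it is nearly free and changes what the virologic part of the safety objective can conclude. The primary endpoint is unaffected.

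**What to change.** In 4.2.2.2, 8.2.2.2.3 and 8.7.1.3, report the endpoint by baseline status:

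- **Below 50 at baseline:** the proportion at or above 50 at Week 16, and the proportion with rebound confirmed by the 7.8.1 repeat test at any post-baseline visit. Requiring confirmation stops a single isolated value from counting.
- **At or above 50 at baseline:** the proportion below 50 at Week 16, and the proportion with a confirmed 1-log increase.
- **All subjects:** the 2×2 table of baseline by Week 16 status.

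Use these definitions to give virologic failure a meaning in 3.2.2.2. For this analysis only, count a subject withdrawn after confirmed rebound with resistance as a failure in the intent-to-treat denominator. Patient management under 7.8 does not change.

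**Cost.** Wording in three lists and the objective, plus one table. No new tests are needed: viral load is scheduled at baseline, Week 4, Week 16 and early discontinuation (Table 6.2.4.1.2), and the repeat test is already in 7.8.1. The drawback is precision. With 18 suppressed entrants, 0/18 has an exact 95% interval of 0 to 18.5% and 4/18 one of 6.4 to 47.6%. These overlap, so the report should present the counts as descriptive.

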#### 6.2.4. Study Procedure

##### 6.2.4.1. Overview

6.2.4.1.1. Subjects who are referred for screening from Part I who meet other eligibility criteria (see table 6.2.4.2.1) will be offered enrollment in Part 2. Those who provide consent will complete HIV Symptom Index (HIV-SI), a validated Patient Reported Outcome survey to assess side effects/quality of life, undergo physical and laboratory examinations, and ART will be switched to DRV/COB/FTC/TAF (Syntuza). For subjects who were not suppressed at their last lab evaluation, an HIV genotype will be performed prior to enrollment. Subjects who do not provide consent to enroll in the study will be referred back to their provider to address issues with tolerance and adherence.

6.2.4.1.2. Subjects will be followed for 16 weeks. During that period, they will be brought back for evaluation at the 4th and 16th week. At those evaluations, they will again complete the PRO and adherence surveys to assess tolerability and adherence. At the evaluations, they will also be monitored for safety and effectiveness via physical exams and laboratory studies. See Table 6.2.4.1.2

6.2.4.1.2.1. Labs at each visit: Complete Blood Count, Complete Metabolic Panel, Urinalysis, CD4 panel, HIV1 Quantitative viral load. If subject is of childbearing potential, urine pregnancy will be performed.

6.2.4.1.2.1.1. Special situations: If HIV viral load is >200 prior to baseline and not accompanied by recent genotype, a genotype will be performed.

6.2.4.1.3. Interim analysis will be performed when all subjects have completed 1 month evaluation or when 10 subjects have completed 4 month evaluation, whichever comes first.

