#### **7.6.2. Grades 1 and 2 Clinical Event or Laboratory Abnormality**

7.6.2.1. Continue study drug at the discretion of the Investigator

#### **7.6.3. Grade 3 Clinical Event or Laboratory Abnormality**

7.6.3.1. For Grade 3 clinical event or clinically significant laboratory abnormality, study drug may be continued if the event is considered to be unrelated to study drug.

7.6.3.2. For a Grade 3 clinical event or clinically significant laboratory abnormality confirmed by repeat testing that is considered to be related to the study drug, study drug will be withheld until the toxicity returns to  $\leq$  grade 2. When restarting study drug following resolution of the adverse event, the study drug should be restarted at full dose.

7.6.3.3. If following re-challenge with study drug a laboratory abnormality returns to  $\geq$  Grade 3 and is considered to be related to the study drug, then the study drug will be permanently discontinued and the subject managed according to local practice. Recurrence of laboratory abnormalities considered unrelated to the study drug may not require permanent discontinuation.

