#### **7.6.4. Grade 4 Clinical Events or Laboratory Abnormality**

7.6.4.1. For a Grade 4 clinical event or clinically significant laboratory abnormality confirmed by repeat testing that is considered to be related to the study drug, the study drug will be permanently discontinued and the subject managed according to local practice. The subject should be followed as clinically indicated until the laboratory abnormality returns to baseline or is otherwise explained, whichever occurs first.

7.6.4.2. A clinically significant Grade 4 laboratory abnormality that is not confirmed by repeat testing should be managed according to the algorithm for the new toxicity grade.

7.6.4.3. Study drug may be continued without dose interruption for a clinically non-significant Grade 4 laboratory abnormality (e.g., elevated CK after significant exercise or triglyceride elevation on a non-fasting specimen) or a clinical event considered unrelated to the study drug, but must be discussed with the Investigator.

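### The virologic and laboratory safety proportions count only the Week 16 value, so early events that resolve or leave the study are missed, although the safety objective has no such time limit

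*Protocol*

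**What the plan says.** Protocol 3.2.2.2 sets the Part 2 safety objective, to be judged "as determined by the proportion of participants with virologic failure, a change in laboratory parameters, and change in CD4 cell count from baseline". No visit is named for the failure or laboratory component.

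The endpoints that serve it are tied to one visit. Section 4.2.2.2 takes the proportion with HIV-1 RNA of 50 or more "copies/mL at baseline and at Week 16". Section 4.2.2.3 takes the "Proportion of subjects with significant changes at 4 months from baseline in serum creatinine, AST or ALT". The same timing recurs in 8.2.2.2.3 and 8.2.2.2.4 and in 8.7.1.3 and 8.7.1.4.

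Table 6.2.4.1.2 schedules the metabolic panel and viral load at baseline, Week 4, Week 16 and early discontinuation.

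Three rules act on early events:
- **7.6.3.2:** for a confirmed, drug-related Grade 3 event, "study drug will be withheld until the toxicity returns to" Grade 2 or lower, and drug is then restarted.
- **7.6.4.1:** for a confirmed, drug-related Grade 4 event, "the study drug will be permanently discontinued and the subject managed according to local practice".
- **7.8.1:** a rebound is retested within 4 weeks and genotyped if the repeat is 200 or more. Then: "Subject may be withdrawn from the study at investigators discretion if resistance suggested by results".

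For subjects who stop drug, 7.7.3 says that "every attempt should be made to keep the subject in the study", with procedures continued to Week 16.

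**The concern.** There are 12 weeks between the Week 4 and Week 16 visits. An abnormality found at Week 4 prompts action, and that action is meant to resolve it. An endpoint that looks only at Week 16 then scores the subject as having had no event. A subject withdrawn for resistant rebound has no Week 16 viral load at all.

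In both cases the event itself is the reason it goes uncounted, so the loss is informative. What is at stake is whether the two headline safety proportions answer objective 3.2.2.2, which asks how many subjects had virologic failure or laboratory change. As worded, they answer a narrower question: how many were abnormal at Week 16.

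**Working it through.** **The plan's own figure.** The protocol gives no figure for these endpoints. Its only computed figure is the target of 30 in 8.8.2: ln(1 − 0.95)/ln(1 − 0.10) = 28.43, which rounds up to 29 against the stated 30. It serves below only as the denominator.

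**Step 1: what each path scores as worded.**

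| Course of the subject | Week 16 count (4.2.2.2, 4.2.2.3) | Objective 3.2.2.2 |
|---|---|---|
| Week 4 ALT, AST or creatinine event, resolved by Week 16 | not counted | laboratory change |
| The same event, still significantly changed at Week 16 | counted | laboratory change |
| Week 4 rebound, confirmed, re-suppressed by Week 16 | not counted | virologic failure |
| Week 4 rebound, resistance suggested, withdrawn under 7.8.1 | no Week 16 value to count | virologic failure |
| Rebound, kept in the study, still 50 or more at Week 16 | counted | virologic failure |

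Week 16 is itself a post-baseline visit. For one fixed criterion, the number of subjects meeting it at Week 16 therefore cannot exceed the number meeting it at any post-baseline visit. The direction (understatement) is certain as soon as one early event resolves or leaves.

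One limit applies on the virologic side. The 7.8.1 criterion is a rise to 50 or more from below 50, or a 1-log increase in a subject already at 50 or more. A subject viraemic at baseline and unchanged throughout meets 4.2.2.2 but is not a rebound. The two virologic counts complement each other and both are needed.

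**Step 2: size, by illustration.** The protocol gives no event rate and no share of events that resolve or leave, so both are assumed. Let *e* of 30 subjects have an early event, with *k* of them not visible at Week 16, and no other events.

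- Any post-baseline visit: e/30
- Week 16, the *k* events resolved: (e − k)/30
- Week 16, the *k* subjects withdrawn, observed cases only: (e − k)/(30 − k)

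For e = 3, the any-time rate is 3/30 = 10.0% (exact 95% CI 2.1% to 26.5%).

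| k | Resolved | Withdrawn, observed cases |
|---|---|---|
| 0 | 3/30 = 10.0% | 3/30 = 10.0% |
| 1 | 2/30 = 6.7% | 2/29 = 6.9% |
| 2 | 1/30 = 3.3% | 1/28 = 3.6% |
| 3 | 0/30 = 0% (upper limit 11.6%) | 0/27 = 0% (upper limit 12.8%) |

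With zero events the exact upper limit is 1 − 0.025^(1/n), which gives 11.6% for n = 30 and 12.8% for n = 27.

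For e from 2 to 5, the any-time rate runs from 2/30 = 6.7% to 5/30 = 16.7%. The Week 16 count runs from that full value down to 0%.

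**The case against.** A Week 16 landmark is a legitimate choice for descriptive endpoints with no hypothesis test (8.2.2.2, 8.7.1), and several facts limit the loss.

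- **Nothing disappears from the trial.** Laboratory abnormalities that lead to interruption or discontinuation must be recorded as adverse events (7.2.1.1). Data are summarised by visit (8.7.2), so Week 4 is reported. Discontinuations for any reason are a separate endpoint (4.2.2.6).
- **A hold does not mean normal values.** It ends at Grade 2 or lower, and Appendix 4 Grade 2 ALT is 2.6 to 5.0 times the upper limit. Such a subject could still count at Week 16.
- **The SAP is not shown.** It may set the rule for missing Week 16 values and the cut-off for *significant*. Their absence here is no finding. A rule that treats missing as failure would recover the withdrawn rebound.

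All of this stands, but it does not close the gap. By-visit tables do not count subjects across visits. A temporary hold is not a discontinuation. A missing-data rule cannot recover a subject whose Week 16 value is present and normal. The visit is fixed by the protocol, not left to the SAP.

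A reader might go further and infer that the protocol removes subjects with failure or toxicity before Week 16. The text does not support that. No rule withdraws a subject from the study for laboratory toxicity. The hold applies only to confirmed, related Grade 3 events. No rule withholds drug for rebound, although 7.7.2 permits stopping for lack of efficacy. Withdrawal under 7.8.1 is discretionary and tied to resistance.

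A reader might also see a contradiction between 7.8.1 and 7.7.3. There is none: 6.2.4.8.1 asks for every effort at retention and also allows withdrawal where staying is not acceptable to the subject or investigator.

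**Conclusion.** The point holds in limited form. The two safety proportions are Week 16 landmark counts that do not deliver what objective 3.2.2.2 asks for. Week 4 and early discontinuation results already collected are left out of them. Measured against the objective, the omission can only understate the proportions.

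The size cannot be derived from the document. With 3 early events assumed in 30 subjects, 10% is reported as anything between 10% and 0%, depending on how many resolve or leave. Even at 0/30 the upper limit of 11.6% still covers 10%, so the distortion lies mainly in the point estimate. It does not follow that an early harm would go unseen, because the other summaries would show it. The endpoints are descriptive, so the significance level and sample size are unaffected.

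**What to change.** Keep the Week 16 summaries in 4.2.2 and 8.7.1, with observed values unchanged. Add two descriptive proportions for all treated subjects (the dataset in 8.3.4), and state how many have no post-baseline result:

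1. **Creatinine, AST and ALT:** the proportion by worst post-baseline Appendix 4 grade, and the shift from baseline grade, using Week 4, Week 16, early discontinuation and confirmatory results. Section 8.3.2.1 already re-grades the laboratory data. The shift is needed because 6.2.3.1.3 admits AST/ALT up to 3 times the upper limit, which can already be Grade 2.
2. **HIV-1 RNA:** the proportion with confirmed rebound as described in 7.8 at any post-baseline time, with subjects withdrawn for it counted as failures.

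Do not recode a re-suppressed subject as 50 or more at Week 16. That would overwrite an observed value, and the any-time proportion already captures the event.

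The cost is some wording and one more descriptive table from data already collected. The reported rates may look less favourable.
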